## 9.2 Analysis of secondary pharmacokinetic variables

The secondary PK variables in plasma used for PSL are  $C_{max,ss}$  and  $AUC_{\tau}$ .  $C_{max,ss}$  will be determined from the observed concentration and time data.  $AUC_{\tau}$  will be computed using the linear up/log down trapezoidal rule.

Pharmacokinetic parameters ( $C_{max,ss}$ ,  $C_{trough}$ ,  $AUC_{\tau}$ , metabolic ratio based on  $AUC_{\tau}$  ( $MR_{AUC_{\tau}}$ )) of PSL and its two metabolites will be compared between days with OC [Part 1: Day 13 for Sequence A and Day 30 for Sequence B; Part 2: Day 9 for Treatment Sequence A and Day 26 for Treatment Sequence B] and without OC [Part 1: Day 12 for Treatment Sequence A and Day 29 for Treatment Sequence B; Part 2: Day 8 for Treatment Sequence A and Day 25 for Treatment Sequence B] using analysis of variance on the log-transformed parameters and estimation of geometric ratio of PK parameters between days with their 90% CI will be provided. Ping-pong plots will also be produced for each study part for  $C_{max,ss}$ ,  $AUC_{\tau}$ ,  $MR_{AUC_{\tau}}$ ,  $MR_{C_{max,ss}}$ ,  $CL_{ss}$ ,  $t_{1/2}$ , for PSL (with and without OC).

The relationship between individual AUC ratio and individual  $C_{max}$  (with and without PSL) of EE and LN, and the exposure to PSL ( $AUC_{\tau}$ ) will be assessed by scatterplots and linear regression analyses (log-transformed and also untransformed data) presented for each study part.

The estimated slope with 95% CI will be computed. In absence of interaction, intercept and slope will be equal to 0.

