The relationship between individual AUC ratio (with and without PSL) of EE and LN, and the exposure to PSL (AUC_{τ}) will be assessed by scatterplots and linear regression analyses (log-transformed and also untransformed data).

The estimated slope with 95% CI will be computed. In absence of interaction, intercept and slope will be equal to 0.

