## LIST OF ABBREVIATIONS

AE(s)	adverse event(s)
ALT	alanine aminotransferase
ALQ	above the limit of quantification
ANOVA	analysis of variance
AST	aspartate aminotransferase
ASP	all study participants
AUC	area under the curve from time 0 to infinity
AUC 0-t	area under the curve from time 0 to the last quantifiable concentration
AUC 0-12	area under the curve from time 0 to 12h
AUC τ	area under the curve over a dosing interval
BID	twice daily
BLQ	below the limit of quantification
BMI	body mass index
BP	Blood pressure
CI	confidence interval
CL/F	apparent total clearance
CL SS /F	apparent total clearance at steady-state
C max	maximum observed plasma concentration
C max,ss	maximum observed plasma concentration at steady-state
C min	minimum observed plasma concentration
CRF	case report form
CRU	clinical research unit
C trough	plasma trough concentration

---

CSR	clinical study report
CV	coefficient of variation
C-SSRS	Columbia-Suicide Severity Rating Scale
DEM	data evaluation meeting
DDI	Drug Drug Interaction
ECG	electrocardiogram
EDV	Early Discontinuation Visit
EE	Ethinylestradiol
EOS	End of Study
EudraCT	European Union Drug Regulating Authorities Clinical Trials
FDA	Food and Drug Administration
geoCV	geometric coefficient of variation
ICF	Informed Consent form
ICH	International Council on Harmonisation
IMP	investigational medicinal product
IPD	important protocol deviation
LLOQ	lower limit of quantification
LN	Levonorgestrel
MedDRA	Medical Dictionary for Regulatory Activities
$MR_{AUC\tau}$	Metabolic ratio for $AUC\tau$
$MR_{C_{max,ss}}$	Metabolic ratio for $C_{max,ss}$
n	number of study participants number of available observations
NCA	Noncompartmental analysis
OC	Oral contraceptive

PDILI	Potential drug-induced liver injury
PKS	Pharmacokinetic Set
PK	Pharmacokinetic(s)
PK-PPS	Pharmacokinetic-Per Protocol Set
PR	pulse rate
PSL	Padsevonil
PT	preferred term
QTcF	QT corrected for heart rate using Fridericia's formula
RR	respiratory rate
SAE(s)	serious adverse event(s)
SAP	statistical analysis plan
SD	single dosing
sd	standard deviation
SFU	Safety Follow-up
SOC	system organ class
SS	Safety Set
TEAE	treatment-emergent adverse event
TEMA	treatment-emergent markedly abnormal
TFLs	tables, figures and listings
$t_{max}$	time to maximum concentration ( $C_{max}$ or $C_{max,ss}$ )
$t_{1/2}$	terminal elimination half-life
$t_{1/2,ss}$	terminal elimination half-life at steady state

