### 3.9 Changes to protocol-defined analyses

- Changes in the name of analysis datasets (section 9.1 of the protocol):
  - The analysis set “Enrolled set” will be renamed as “All Study Participants” in the SAP and will correspond to all study participants who sign the informed consent form.
  - The analysis set “Pharmacokinetic Per Protocol Set (PK-PPS)” will be renamed as “Pharmacokinetic Set (PK Set)” in the SAP and will still correspond to the protocol definition of PK-PPS.
- For the purpose of the analysis of concomitant medications and adverse events 3 groups will be created, based on the treatment administered. The results will be presented for PSL alone, OC alone and the combination of PSL and OC.
- For the primary PK analysis, ping-pong plots have been added for EE and LN for  $C_{max}$ , and AUC for OC with and without PSL.
- Ping-pong plots have also been added for  $C_{max,ss}$  and  $AUC_{\tau}$ , for PSL and its two metabolites ( [REDACTED] and [REDACTED] ) for PSL with and without OC.
- Ping-pong plots have been added for  $C_{max,ss}$ ,  $AUC_{\tau}$ ,  $MR_{AUC_{\tau}}$ ,  $MR_{C_{max,ss}}$ ,  $CL_{ss}$ ,  $t_{1/2}$ , for PSL (with and without OC).
- Furthermore, the relationship between MR and  $C_{max}$  (with and without PSL) of EE and LN, and the exposure to PSL ( $AUC_{\tau}$ ) will be explored.
- Ctrough and MR based on  $AUC_{\tau}$  of PSL and its two metabolites, will also be compared between days (with OC [Day 13 for Sequence A and Day 30 for Sequence B] and without OC [Day 12 for Treatment Sequence A and Day 29 for Treatment Sequence B] using analysis of variance on the log-transformed parameters and estimation of geometric ratio of PK parameters between days with their 90% CI will be provided.
- Furthermore, the relationship between individual  $C_{max}$  (with and without PSL) of EE and LN and the exposure to PSL ( $AUC_{\tau}$ ) will be assessed by scatterplots and linear regression analyses.
- According to the protocol, the occurrence and incidence of AEs will be summarized by treatment sequence according to the intake of PSL (pretreatment or treatment-emergent) and

by intensity or relationship to PSL. As the relationship to PSL alone is not documented in the CRF, the relationship to study medication (PSL, PSL+OC, and OC) will be analyzed. Consequently, the definition of TEAE will be related to treatment (PSL, PSL+OC, or OC) and a TEAE will be attributed to a treatment according to the start date.

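### The SAP extends the exposure-response regression to Cmax but names the individual Cmax and not the with/without-PSL ratio, so its slopes do not isolate the interaction and its stated null cannot apply

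*SAP*

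**What the plan says.** Protocol 9.3 plans one exposure-response analysis: "The relationship between individual AUC ratio (with and without PSL) of EE and LN, and the exposure to PSL" (AUCtau). The dependent variable is a within-woman ratio, and Cmax is not mentioned.

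SAP 9.2 widens the sentence. It now begins "The relationship between individual AUC ratio and individual" Cmax, with the with/without-PSL parenthesis placed after Cmax. The method is that these relationships "will be assessed by scatterplots and linear regression analyses (log-transformed and also untransformed data) presented for each study part". One null is given for everything in the paragraph: "In absence of interaction, intercept and slope will be equal to 0".

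SAP 3.9 lists two related additions:

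- One begins "Furthermore, the relationship between individual" Cmax and names scatterplots and linear regression, again without the word ratio.
- The other begins "Furthermore, the relationship between MR and" Cmax and continues "with and without PSL) of EE and LN, and the exposure to PSL" (AUCtau). It says only that the relationship will be explored. SAP 9.2 has no matching MR analysis of EE or LN.

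The SAP's abbreviation list expands MR only as "Metabolic ratio for" AUCtau or Cmax,ss of PSL.

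**The concern.** The analysis is meant to show whether women with higher PSL exposure lose more OC exposure. Only a within-woman contrast answers that. A woman's raw Cmax also reflects her body size, absorption and clearance, and her PSL AUCtau may share some of these determinants. A slope of raw Cmax on AUCtau can then differ from zero with no interaction, or mask a real one.

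According to SAP 1, only Part 1 will be reported. With 14 women, a CV of 16% and a true ratio of 0.90, the power of the primary equivalence test is about 58%. If the primary result is inconclusive, readers may look to supportive slopes for direction, so those slopes should estimate the right quantity.

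**Working it through.** **Inputs from the documents.** Part 1 has n = 14 (SAP 2.2). The intra-subject CV is 16% for EE Cmax and 10% for LN Cmax (SAP 2.3). On the log scale, 16% is √ln(1 + 0.16²) = 0.159, rounded to 0.16 below.

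**Inputs assumed, because the documents give none.** SD of log PSL AUCtau 0.4; between-woman SD of log Cmax 0.3 to 0.4; correlation ρ between a woman's underlying log Cmax and her log PSL AUCtau from −0.3 to 0.5.

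**The plan's own figure.** No figure is stated for this regression. The 16% CV comes from the sample-size statement, which reproduces. Crossover TOST power (SE = 0.159·√(2/n), df = n − 2, 0.05 per side, true ratio 0.90) is 79.99% at 24, 82.9% at 26 and 91.1% at 34. So 26 and 34 are the smallest even sizes for 80% and 90%.

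**Step 1: what each slope estimates.** In each woman, log Cmax(with) = log Cmax(without) + log ratio. Least squares is linear in the dependent variable, so in the same women

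slope(with) = slope(without) + slope(ratio).

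In Part 1 the OC-alone Cmax is measured on Day 1 in Sequence B, before PSL starts on Day 18, and on Day 34 in Sequence A, after the 14-day washout. If the washout is adequate, slope(without) carries no interaction. Slope(with) mixes both components. Only slope(ratio) isolates the interaction. No value of ρ is needed for this step.

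**Step 2: size of the between-woman part.** With no interaction, the expected raw slope is ρ × SD(between) / SD(log AUCtau). A true interaction slope of −0.20 adds −0.20 to the with-PSL slope. Rejection rates are from 20,000 simulated trials of n = 14.

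| SD between | ρ | Raw slope, no interaction | 95% CI excludes 0 | With-PSL slope if truth is −0.20 |
|---|---|---|---|---|
| 0.3 | −0.3 | −0.22 | as for +0.3, by symmetry | −0.42 |
| 0.3 | 0 | 0.00 | 5% | −0.20 |
| 0.3 | 0.3 | +0.22 | 15% | +0.03 |
| 0.4 | 0.3 | 0.3 × 0.4/0.4 = +0.30 | 17% | +0.10 |
| 0.4 | 0.5 | 0.5 × 0.4/0.4 = +0.50 | 40% | +0.30 |

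(0.3 × 0.3/0.4 = 0.225 lies behind the first and third rows.) In every row the log-ratio regression averages 0 with 5% rejection under no interaction, and −0.20 when that is the truth. A second run with both SDs at 0.35 gave null slopes of 0.30, 0.50 and 0.70 at ρ = 0.3, 0.5 and 0.7, with rejection of 16%, 38–39% and 74%. The ratio stayed at 0 and about 5%.

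**Step 3: precision at ρ = 0.** SE ≈ residual SD / (0.4 × √(n − 3)), and 0.4 × √11 = 1.327.

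- EE, raw Cmax: √(0.3² + 0.16²) = 0.34; 0.34/1.327 = 0.26.
- EE, ratio: √2 × 0.16 = 0.226; 0.226/1.327 = 0.17.
- LN (log SD 0.10): raw √(0.3² + 0.10²) = 0.316, SE 0.24; ratio √2 × 0.10 = 0.141, SE 0.11.

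**Step 4: the stated null.** For a raw Cmax the intercept is a concentration level (or its log), so zero is not its no-interaction value. For an untransformed ratio, no interaction means a ratio of 1 at every exposure: intercept 1, slope 0. Intercept 0 with slope 0 is right only for a log-transformed ratio. The SAP plans both scales and gives one null.

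**Step 5: MR.** SAP 3.1 lists the assayed analytes as EE, LN, PSL and PSL metabolites. SAP 9.3 lists MR for the PSL metabolites and not for EE or LN. An MR of EE or LN therefore has no metabolite to be formed from.

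**The case against.** The strongest reply is that a word was dropped. In the protocol the with/without parenthesis qualifies ratio, and SAP 9.2 reuses it. The zero null makes no sense for a raw Cmax, and SAP 9.1 speaks of individual ratios for both AUC and Cmax. This is plausible, and it may be what was meant. But the wording without ratio stands in two places in the SAP, beside an AUC ratio in the same sentence of 9.2, and a programmer could implement it literally. The same edit settles the matter either way.

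The stakes are also limited, and that stands. No decision rule uses this regression. SAP 1 restricts reporting to a subset of Part 1 outputs, which may not include it. Even the correct ratio regression would detect a slope of −0.20 in only about 21% of trials.

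Four stronger readings are tempting, and the documents do not support them:

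- *The SAP has abandoned the ratio.* It keeps the AUC ratio; only the added Cmax lacks the word.
- *The slopes say nothing about the interaction.* That is exact only for the OC-alone Cmax. If both log slopes are reported in the same women, their difference equals the ratio slope.
- *The slope must be positive, or have the wrong sign.* The values +0.22 to +0.50 come entirely from an assumed positive correlation. At zero correlation there is no bias, and a negative correlation reverses it.
- *The SAP regresses an impossible MR of EE and LN.* The MR item is only in SAP 3.9 and is to be explored, with no regression named. The words about EE and LN may qualify Cmax alone, with MR meaning the PSL metabolic ratio. The text is ambiguous.

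**Conclusion.** The concern holds as a specification error in the added Cmax regression. As written, the OC-alone slope carries only between-woman association, the with-PSL slope adds that association to the interaction, and the zero null does not fit the variable. These conclusions follow from algebra and the sampling schedule, given an adequate washout.

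The size is uncertain. Under the assumed SDs, the no-interaction slope is 0 at zero correlation, +0.22 to +0.50 at correlations of 0.3 to 0.5, and negative for a negative correlation. The loss of precision does not need a correlation: an SE of about 0.26 against 0.17 for EE at n = 14 and a between-woman SD of 0.3, but this also rests on the assumed SDs. The AUC-ratio regression, the primary ANOVA and its 90% CI are untouched. The analysis is exploratory, so this is a correction worth making and not a threat to the trial's main conclusion.

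**What to change.** 1. In SAP 9.2 and in the SAP 3.9 bullet that names the Cmax regression, make the dependent variable the individual Cmax ratio (OC+PSL / OC alone) of EE and LN, alongside the AUC ratio already in 9.2.
2. In the other SAP 3.9 bullet, remove MR or state that it is the PSL metabolic ratio, and drop the Cmax item there as a duplicate.
3. In SAP 9.2, limit the zero null intercept to log-transformed ratios and give 1 as the null intercept for untransformed ratios. Protocol 9.3 carries the same single null, so SAP 3.9 can record this as a clarification.

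The cost is SAP wording only. The Cmax values with and without PSL are already derived for the primary analysis, and no sampling or sample size changes.

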## 2.3 Determination of sample size

Lack of PK interaction in this study will be concluded if 90% confidence intervals for both AUC and  $C_{\max}$  geometric means ratios (with/without PSL) of LN and EE are included in the 80% to 125% bioequivalence range.

In a previous OC interaction study conducted by UCB with brivaracetam (N01282), an intra-subject coefficient of variation of 10% for  $AUC_{\tau}$  for both EE and LN (including  $C_{\max}$ ) and 16% for  $C_{\max}$  was observed for EE.

Provided that the ratio of the expected means for test (with PSL) and reference (without PSL) is included in the range [0.90, 1.10] and for a type-I error of 0.05 and an intra-subject coefficient of variation of 16%, a total sample size of 34 study participants should allow at least 90% power for the assessment of lack of interaction (or 26 study participants for 80% power).

A total of 40 study participants will be randomized: Part 1 (PSL 400mg BID) will include 14 study participants and will allow a good estimate of the different ratios of PK parameters. Part 2 (PSL 200mg BID) will include 26 study participants (13 study participants in each sequence). Assuming no drop-outs, a decrease of 10% in PK parameters of OC and intrasubject coefficient of variation of 16%, this will allow 80% power for assessing lack of PK interaction.

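### The no-interaction reference of intercept 0 is wrong for the regression of the untransformed EE/LN ratio on PSL exposure; on that scale it is 1

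*SAP*

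**What the plan says.** Protocol 9.3 sets out the analysis as "The relationship between individual AUC ratio (with and without PSL) of EE and LN, and the exposure to PSL", the latter measured by AUCτ. SAP 9.2 keeps it and adds Cmax: it opens with "The relationship between individual AUC ratio and individual" Cmax, with and without PSL, and says the relationships "will be assessed by scatterplots and linear regression analyses (log-transformed and also untransformed data"), for each study part.

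The only regression estimate that either document commits to is the slope: "The estimated slope with 95% CI will be computed". The next sentence, identical in both, gives the benchmark for reading the fits: "In absence of interaction, intercept and slope will be equal to 0". It is not limited to the log-transformed fit, and the untransformed response is not defined as a difference from 1. SAP 3.9, which lists departures from the protocol analyses, does not correct it.

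**The concern.** One benchmark is given for two scales on which the null value of the response differs. A with/without ratio that shows no effect equals 1, and this is how the rest of the plan treats it: SAP 2.3 and 9.1 judge the ratio against 80% to 125%, and the fallback in 9.1 is a ratio above 0.7. The log of 1 is 0, but 1 itself is not 0.

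Anyone who reads the intercept of the untransformed fit against the stated 0 would take a result of about 1, which is what no interaction produces, as a departure from no interaction. Only the reading of that one number is at stake.

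**Working it through.** **Inputs from the documents**
- Response: individual ratio R = exposure with PSL / exposure without PSL (Protocol 9.3, SAP 9.2; direction from SAP 2.3).
- Predictor: PSL AUCτ.
- Intra-subject CV (SAP 2.3): "an intra-subject coefficient of variation of 10% for" AUCτ of both EE and LN, and 16% for EE Cmax.
- Part 1 size: n = 14 (SAP 2.2).

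**Assumed, because not given:** between-participant CV of PSL AUCτ of 30% to 50%.

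**Step 1. The log ratio reproduces the stated benchmark.** No interaction means R = 1 at every PSL exposure, so log R = 0 everywhere. A straight line through a constant 0 has intercept 0 and slope 0, as the plan says.

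**Step 2. The untransformed ratio does not.** R = 1 everywhere, and a straight line through a constant 1 has intercept 1 and slope 0. Least-squares fits to noise-free data at n = 14 and n = 26 give intercept 1.000 and slope 0 untransformed, and 0 and 0 for the log-log fit.

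**Step 3. Allow for within-subject noise.** With no interaction, and a ratio independent of PSL AUCτ, log R ~ N(0, 2σ²) with σ² = ln(1 + CV²). The mean of a lognormal ratio is exp(2σ²/2) = exp(σ²) = 1 + CV², and the least-squares intercept is unbiased for it:
- CV 10%: 1 + 0.10² = 1.0100
- CV 16%: 1 + 0.16² = 1.0256

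**Step 4. Illustration at n = 14.** 100,000 no-interaction data sets were simulated per setting, with lognormal PSL AUCτ and 95% CIs from t with 12 degrees of freedom. The plan calls for no intercept CI; it is used here only to show how far apart the two benchmarks are.

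| PSL AUCτ CV (assumed) | EE/LN CV | Mean intercept, untransformed | Intercept CI excludes 0 | Intercept CI excludes 1 | Slope CI excludes 0 |
|---|---|---|---|---|---|
| 30% | 10% | 1.011 | 99.85% | 5.04% | 5.02% |
| 30% | 16% | 1.025 | 95.25% | 4.95% | 4.90% |
| 50% | 10% | 1.010 | 100.00% | 4.94% | 4.99% |
| 50% | 16% | 1.026 | 99.81% | 5.00% | 4.90% |

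In the log-log fit, the intercept CI excludes 0 in 5.00%, 4.86%, 4.99% and 4.89% of data sets (same order), and the slope CI in 4.97%, 4.86%, 5.00% and 4.89%. So the stated benchmark works for the log intercept and for the slope on both scales. It fails for the untransformed intercept, where 1 works.

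**The case against.** The strongest reply is that nothing planned depends on the error. Only the slope is to be estimated with an interval, and its reference of 0 is correct on both scales. No test, threshold or decision uses the intercept, and the lack-of-effect conclusion in SAP 9.1 does not use this regression. SAP 1 also limits reporting to Part 1 and a subset of outputs, without saying whether this one is included. All of that stands, and it is why the point is minor. It does not make the sentence right: the plan chose to state an intercept benchmark, and for one of its two fits that benchmark is false.

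A second reply is that the text does not name the variable left untransformed. If the log ratio were regressed on both log and untransformed PSL AUCτ, intercept 0 would hold in both fits. Neither document says this, and the less strained reading is that both variables are analysed on both scales. If the narrower reading was meant, the sentence still needs to say so.

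Three smaller points also stand. The simulated percentages describe an interval that is not planned and rest on an assumed PSL AUCτ spread. The 16% CV was observed for EE Cmax, so for the AUC ratio only the 10% rows use the observed CV. And intercept 1 is the noise-free value; the expected value is slightly higher, at 1 + CV².

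**Conclusion.** The concern holds. For the untransformed ratio the no-interaction intercept is 1, not 0; allowing for lognormal noise, its expectation is 1.010 at CV 10% and 1.026 at CV 16%. At n = 14, an intercept CI, if one were computed, would exclude the stated 0 in 95.3% to 100% of no-interaction data sets and exclude 1 in about 5%.

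The algebra rests only on reading the untransformed response as the ratio itself. The percentages also assume a PSL AUCτ CV of 30% to 50% and a ratio unrelated to PSL exposure. The log-scale reference and both slope references are correct, and the primary conclusion is unaffected. This is a low-priority correction of an interpretive sentence.

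**What to change.** In SAP 9.2, replace the benchmark sentence with: *For the log-transformed ratio, absence of interaction corresponds to intercept 0 and slope 0; for the untransformed ratio, to intercept 1 and slope 0.* Because Protocol 9.3 has the same sentence, record the correction in SAP 3.9. Before database lock this goes in by SAP amendment, as SAP 1 requires for changed analysis definitions; after lock, a note in the CSR is enough. The cost is one sentence and one list entry, with no programming.

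A related wording point depends on intent. SAP 9.2 refers to individual Cmax rather than a Cmax ratio, as do the two SAP 3.9 bullets that begin "Furthermore, the relationship between MR and" and "Furthermore, the relationship between individual". If a ratio is meant, write Cmax ratio in all three places; for a raw Cmax, neither 0 nor 1 is a meaningful no-interaction intercept. That is one added word in each place, but any output already programmed on raw Cmax would need its response variable changed, and the documents do not show which was programmed.

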## 9.3 Analysis of other pharmacokinetic variables

The other steady-state PK parameters for PSL are  $CL_{SS}/F$ ,  $C_{min}$ ,  $t_{max}$  and  $t_{1/2}$ .

The other steady-state PK parameters for the two PSL metabolites [REDACTED] include  $C_{max,ss}$ ,  $AUC_{\tau}$ ,  $t_{max}$ ,  $t_{1/2,ss}$ ,  $C_{trough}$ ,  $MR_{AUC_{\tau}}$ ,  $MR_{C_{max,ss}}$ .  $C_{max,ss}$  will be determined from the observed concentration and time data.  $AUC_{\tau}$  will be computed using the linear up/log down trapezoidal rule.

The other PK parameters for EE and LN (single-dose oral contraceptive containing EE and LN) include  $t_{max}$ ,  $AUC_{0-t}$ ,  $t_{1/2}$  and  $CL/F$ .

The other PK parameters will be summarized by study part and treatment using descriptive statistics (number of available observations [n], arithmetic mean, median, standard deviation, minimum, maximum, geometric mean, geometric CV and 95% CI for the geometric mean [assuming lognormally distributed data]).  $t_{max}$  will only display the number of available observations [n], median, minimum, and maximum.

Ping-pong plots will also be produced for  $C_{max,ss}$  and  $AUC_{\tau}$  separately for each study part for the two PSL metabolites ([REDACTED]).

